## 1. Concept Synopsis and Study Schema

The South African National Blood Service (SANBS) uses both Nucleic Acid Testing (NAT) and serology to screen blood donors for Human Immunodeficiency Virus (HIV) and Hepatitis-B Virus (HBV). Positive NAT precedes seroconversion by days to weeks in newly acquired HIV and HBV infections; a combined testing strategy using NAT and serology therefore, confers the ability to detect acute infection and discriminate between recent (incident) and more remotely acquired (prevalent) infection. Additional post-seroconversion techniques that exploit antibody maturation kinetics such as Limiting Antigen Avidity assay (LAg Avidity) can further assist to classify HIV seroconverters as recently acquired or prevalent infections. Hepatitis B core antibody (anti-HBc) testing of NAT only and NAT and serology concordant HBV infections allows further classification of HBV infections as recently acquired or prevalent infections. Studies suggest that the risk factors for HIV among incident infected blood donors may differ from those of prevalent infection. Similarly risk factors for recently acquired HBV may be different than for prevalent HBV infections. The demographic and behavioural risks associated with incident HIV and incident HBV infection have, as yet, not been formally assessed in South African blood donors using analytical study designs. A better understanding of these risk factors is imperative to transfusion safety; this information can be used to improve exclusion of high-risk donors through targeted questions on the donor history questionnaire, and may have critical importance for other sub-Saharan Africa countries with similar risk profiles and insufficient resources for NAT testing. Moreover, this study will identify any shift in the epidemiologic characteristics of infected donors that may have occurred in South Africa; it also imparts the ability to prospectively monitor genetic characteristics of recently acquired infections through genotyping and drug resistance profile testing. A contemporary understanding of the current risk profile for HIV and separately for HBV are critical not only to blood banking, they also directly inform broader public health initiatives in South Africa. HBV infection impacts HIV progression in co-infected individuals and vice versa. In this study the potential for identifying persons who are recently infected with both HIV and HBV also exists. Finally, the ability to identify recent HIV infections provides a unique opportunity to study the biology, host response and evolution of HIV disease at time points proximate to virus acquisition.

In order to determine risk factors for incident HIV and HBV infections (Objective 1) we will conduct a frequency matched (stratified sample) case-control study with two case groups: incident HIV infected blood donors; and incident HBV infected blood donors, both to be compared to infectious marker negative controls. Cases and controls will be accrued from a geographically diverse donor pool. We will further characterize HIV clade and drug resistance profiles and determine viral loads in all cases of incident HIV infection, and HBV genotype and viral load in all incident HBV infections (Objective 2), and follow incident and elite controller HIV infections prospectively for three additional visits at 2, 3, and 6 months following index donation (Objective 3).

## Protocol

### 3. Background and Significance

HIV Infection is presently the foremost public health concern in South Africa owing to a nationwide prevalence of 10.9% in persons over 2 years of age and up to 30% among pregnant women. In this environment of high HIV prevalence, the South African National Blood Service (SANBS) must collect more than 800,000 units of whole blood each year from a pool of more than 350,000 donors in order to contend with the country's growing transfusion need. A number of strategies have been successfully implemented by SANBS in order to protect against HIV in the blood supply. Donor selection is central to this process and is achieved through the exclusive use of voluntary, non-remunerated donors, exclusion of high-risk donors identified through the donor history questionnaire and a product triage policy that excludes use of higher risk, first-time donations for component production. An accurate risk assessment of prospective blood donors is contingent upon contemporary knowledge of behavioural risk factors associated with recent HIV infection, since recent infection is more likely to escape detection by available laboratory tests. The selection process consequently hones in on high-risk behavioural exposure (e.g. multiple sexual partners, sexually transmitted diseases, injection drug use, sexual assault) etc. Failure to capture high-risk donors through this primary interface is in part addressed through universal laboratory screening for antibodies against HIV (HIV-1 and HIV-2) and HBV surface antigen (HBsAg) as well as HIV viral RNA and HBV viral DNA using individual donation- nucleic acid testing (ID-NAT). Although laboratory testing bolsters the safety net, it should not distract from the importance of donor selection, particularly in view of residual risk such as possible viral subtypes or very early infection that could escape laboratory capture.

National surveillance of HIV risk in Africa has traditionally focused on prevalent rather than incident infection; this holds implications for prevention planning and evaluation. Prevalent infection, although more amenable to measure, provides a skewed assessment of disease profile, particularly in view of expanding antiretroviral coverage that prolongs survival. Incidence surveillance reflects a more accurate representation of currently relevant risk factors given the proximity to recent infection. This has consequently been adopted effectively in the United States and other industrialized countries. Unfortunately, there is a lack of HIV or HBV incidence data, particularly in resource-poor settings and specifically in sub-Saharan Africa where these diseases are prominent. Furthermore, comparative analyses of incident vs. prevalent risk factors are few. The assumption that incident risk factors parallel those of prevalent infection is not necessarily accurate. This was demonstrated in a study by McFarland et al in Zimbabwe, whereby age and marital status reversed their direction of association with respect to HIV incidence vs. prevalence. This may reflect a shift in the epidemiology of HIV infection.

The use of ID-NAT by SANBS provides a unique opportunity to identify very recent HIV and HBV infections with a high degree of accuracy. Universal screening of donations by parallel testing for nucleic acids and serological assays can accurately gauge incidence given known thresholds of detection by NAT and serology. In the event that HIV is newly acquired, positivity by ID-NAT (5-10 days post-infection) precedes antibody positivity (detectable at about 21 days) by over 10 days; these so-called “NAT-yield” HIV infections refer to incident or recently acquired infections that have not yet stimulated an antibody response. Over more than 5 years (2005-2010), 165 HIV NAT-yield incident positive cases have been identified at SANBS.

Following infection by HIV or Hepatitis B virus there is a time known as the “eclipse” phase when the infection is not widely disseminated and therefore is not detectable in blood. This time period is different for each infection. Once the infection is established the risk of transmission to another individual increases as plasma viremia increases during the ramp-up phase. After progressing through this stage of infection, the presence of an infection can be determined based on the ability of available methods to identify it. Although ID-NAT testing is imperative to early detection of HIV, there remains a narrow “window period” that eludes current laboratory testing and an even longer window period for HBV infection. This underscores the importance of donor selection as the primary means to capture the high-risk donor prior to appearance of the first detectable viral marker.

In addition to detection of relatively rare NAT yield infections, a number of other methods have been used to gauge HIV incidence, each of which has both strengths and weaknesses, reflecting a balance between logistical ease vs. biological plausibility. These include prospective study, mathematical modeling, serologic testing algorithms for recent HIV seroconversion (STARHS or BED) and laboratory testing platforms that specifically target pre-seroconversion acute infection (HIV RNA or p24 antigen). Prospective evaluation is cost, labor and time intensive, as well as participant to bias; a consented cohort of HIV negative participants is informed of risk, thereby compromising true incidence estimation. Mathematical modeling, although logistically simpler than other methods, relies on both availability and quality of collected data, while interpolating gaps with statistical assumption. The post-seroconversion serological methods i.e. STARHS are particularly useful as they allow incidence estimation via cross-sectional design. STARHS are based on the understanding that following HIV seroconversion, there are described changes in the antibody levels, avidity, class/subclass type and epitope specificity that can reliably be used to backdate incidence. An example of STARHS is the less-sensitive enzyme immunoassay (LS-IA) or “detuned assay” on which early/incident infections are no longer detected by conventional assays. Rapid format detuned testing provides a good indication of incident infection and is increasingly being used. In addition, there is a new Limiting Antigen (LAg) Avidity assay which was recently developed by the CDC and is now commercialized for definitive estimation of HIV incidence.

Similarly for HBV, the window period for HBV ID-NAT from the time of potential infectivity that could lead to infection transmission to the ability of current technology to detect is approximately 15 days and HBV ID-NAT positivity precedes Hepatitis B surface antigen (HBsAg) positivity by approximately 17 days (pre HBsAg window period 32 days from potential infectivity) on average. If a donation tests HBV-NAT positive, HBsAg positive, and anti-HBc negative, the infection is also recently acquired (approximately between 32 and 95 days). SANBS identified 476 HBV ID-NAT yields in 5 years however over 50% were also anti-HBc positive, indicating prevalent versus recently acquired infection. Thus, there were approximately 216 true HBV ID-NAT yields in the five year period, resulting in 40-45 individuals per year that were confirmed “window period” donors. In addition SANBS detected 3414 concordant HBV-NAT positive and HBsAg positive donations of which approximately 5% (170) were anti-HBc negative in five years, giving an additional 30-35 incident infections per annum.

The significance of this study is related to its three objectives: One, determination of demographic and behavioural risk factors for incident HIV and HBV hold great promise for informing targeted prevention measures by blood banks and public health authorities. The potential for identifying persons who are recently infected with both HIV and HBV also exists. In countries where the two viruses are highly endemic the rate of co-infection can be as high as 25%. In recent years, approximately 2.4 % of those SANBS blood donors with confirmed HIV or HBV infection have been co-infected. Prospective collection of incidence data allows for measurement of secular trends and the methodological approaches of behavioural and molecular surveillance we will use may also be of value to other countries with generalized HIV and HBV epidemics in Africa and Asia. Two, we will determine the viral subtype and drug resistance profile of all recently acquired HIV infections, and the genotype of recently acquired HBV infections, allowing study of viral evolution, viral fitness and pathogenicity. While we expect few HIV-HBV co-infections, persons with co-infection are known to have up to five-fold faster disease progression and so efforts to understand the epidemiology of both HIV and HBV, among individuals who are co-infected within the SANBS donor population has the potential for direct impact on public health and health care services in South Africa. In addition for HIV we will be able to determine the frequency at which drug-resistant strains are being transmitted in the population which has clear implications for changing pharmacogenetics and appropriate antiretroviral medicines. Three, evaluation of donors with recently acquired HIV infection and “elite controllers” (HIV antibody positive, ID-NAT negative infections) at multiple time points will be valuable to virologists and immunologists studying the natural history of early HIV infection. These studies will be useful in identifying appropriate HIV drug therapy regimens for this context, as well as strategies for producing an effective HIV vaccine, which has eluded 30 years of HIV research.

#### **4. Objectives**

1a: To identify the demographic and behavioural risk factors associated with incident HIV infection (based on “NAT yield” or LAg Avidity testing) among blood donors in South Africa.

Hypotheses: 1) The risk factors for incident HIV in blood donors in South Africa will include a recent change in sexual partner, older male/younger female sexual partnership, a greater number of recent sexual partners, unprotected receptive anal intercourse, and lower socioeconomic status.

1b: To identify the demographic and behavioural risk factors associated with incident HBV infection among blood donors in South Africa identified as “NAT-yields” or concordant serology and NAT positive and anti-HBc negative.

Hypotheses: 1) The risk factors for incident HBV in blood donors in South Africa will include greater number of recent sexual partners, recent scarification/tattoo/body markings, and history of personal contact with an HBV-infected person.

2a: To determine HIV subtype and drug resistance profiles among HIV positive donors with recently acquired infection based on year of donation and site of collection, and examine findings with donor demographics and risk behaviors derived in Objective 1.

Hypotheses: 1) The proportion of donors identified with incident HIV infection containing drug resistance mutations will be positively related to the proportion of HIV-positive individuals receiving anti-retroviral therapy at a population-level in South Africa

2b: To determine HBV genotype profiles among HBV positive donors with recently acquired infection based on year of donation and site of collection, and correlate findings with donor demographics and risk behaviors derived in Objective 1

Hypotheses: 1) Incident HBV infections will show differences in genotypes with genotype E increasing when compared to public health data on prevalent infections.

3: To prospectively characterize the virology, immunology and natural history of incident HIV infection among a cohort of recently infected blood donors and a small group of elite controllers in South Africa.

#### **4.1 Study Population**

We will conduct a case-control study of risk factors and molecular surveillance for incident HIV and HBV infections in blood donors in South Africa. Accrual, enrollment and follow-up is planned to occur during the period of 3 years (April 2014 – March 2017).

*Our Two Case Groups* will be: (1) 300 incident HIV infected SANBS blood donors, as established through either combined ID-NAT/serology (“NAT yield”) or LAg Avidity assay testing, and (2) 150 incident HBV infected SANBS blood donors, as established through combined ID-NAT/serology (“NAT yield”) and anti-HBc negative testing.

*Controls* will comprise a sample of up to 900 SANBS blood donors who are negative for all infectious markers for which SANBS currently tests and that (a) come from the same geographic areas as the cases (distributed across up to 5 of the 7 regional zones within SANBS) and will further be frequency matched for (b) population group (race), and (c) age. We will enroll three controls for each incident HIV case. These participants will serve as controls for HBV cases also.

*Prospective Cohort:* Approximately 50 persons with very recent HIV infection (NAT yield only) and up to 20 elite controllers identified during this study (mid-2014 – mid-2017) will also be eligible for enrollment in a six month prospective longitudinal study with samples collected for PBMC and other specimen preparations as soon possible after the index donation followed by additional specimen collection at 2, 3 and 6 months.

#### **4.1.1 Inclusion Criteria**

For Objective 1a cases: allogeneic whole blood donors that test positive for incident HIV infection (per NAT or LAg Avidity) at a participating SANBS blood centre during the period of enrollment. For Objective 1b cases: allogeneic whole blood donors that test positive for incident HBV infection at a participating SANBS blood centre during the period of enrollment.

For Objective 1a and 1b controls: donors who successfully donated and are negative for all infections for which SANBS screens (HIV, HBV, HCV, and syphilis).

All participants must be able and willing to provide informed consent and complete the ACASI in the study language, English.

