### **Procedures for donors with ID NAT yield results**

Blood specimens will be tested at either of the two donation testing centres and the results entered in to the centralized database. Donors will be recruited into the study at the time of return to the blood centre for notification. In addition to the standard tubes collected for confirmation of infection (described below) one 9mL sample will be collected. Once the samples have been collected, the donors will be approached for participation and enrolled into the study. Those interested will undergo a written informed consent process with study staff. Following provision of consent, participants who agree will complete the ACASI research questionnaire. Participants whose confirmatory laboratory results are positive for either incident HIV or incident HBV will be allocated as cases. Participants whose infections are subsequently not confirmed will be excluded from analysis.

If it is not possible to make follow-up notification appointments with the donors at the time of collecting the samples for infection confirmation, follow-up appointments will be made as soon

as the results become available. A similar process will be followed as with the initial letter and telephone contact of the donor.

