**Cases Objectives 1 and 2:** The prospective enrollment will build on the existing notification mechanism with additional research nurse staff; we will consent and enroll donors during the retest visit during which they will receive pre-test counseling and be informed of the likelihood of being either HIV or HBV positive (**Consent in Appendix 2**). Following the provision of written informed consent and enrollment, participants will complete the ACASI questionnaire. Although

we plan to administer the ACASI questionnaire immediately following enrollment, we will provide study participants the option of returning to enroll and complete the interview at a later date.

For recent HIV (NAT yield and LAg Avidity recent) and recent HBV (NAT yield and HBsAg positive/anti-HBc negative) infections, all eligible cases will be approached for potential enrollment into the study since we anticipate that no more than 50% of those individuals with a recent infection will return to SANBS for their results following an index donation, but that we will have high success in enrolling these individuals into the study

**Controls:** Controls will be identified from among donors who are negative for all infections for which SANBS screens (HIV, HBV, HCV, and syphilis), and who are stratum-matched by blood centre, age within 5 years, population group. (**Consent in Appendix 3**).

We are proposing on-site recruitment of controls, meaning recruitment of potential controls following successful whole blood donation. To enhance our ability to recruit controls that will be able to be *post-hoc* matched on geographic region, population group, and age, we will select donation sites (both fixed and mobile clinics) with donor characteristics that are similar to donors who are incident HIV-positive. Following completion of the donation, we will invite random donors at predetermined collection sites that have similar demographic characteristics to enrolled cases, to participate in the risk factor study by completing the ACASI. Following completion of testing, donors who are negative for all infections for which SANBS screens will be included in the study.

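### Controls, but not cases, must be negative for syphilis and HCV, which can bias odds ratios upward: little for common exposures under assumed marker prevalences, more for rare ones

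*Protocol*

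**What the plan says.** Section 1 sets out two case groups, "both to be compared to infectious marker negative controls". Section 4.1.1 defines those controls as "donors who successfully donated and are negative for all infections for which SANBS screens (HIV, HBV, HCV, and syphilis". The same condition recurs in sections 4.1, 4.2.2 (Control Recruitment and Enrollment) and 4.3, and in the Controls paragraph of section 4.2.2 (Participant Enrollment): "Following completion of testing, donors who are negative for all infections for which SANBS screens will be included in the study".

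For cases, section 4.1.1 asks for "allogeneic whole blood donors that test positive for incident HIV infection (per NAT or LAg Avidity") or for "allogeneic whole blood donors that test positive for incident HBV infection at a participating SANBS blood centre". Section 4.2.1, on NAT-yield donors, adds: "Participants whose confirmatory laboratory results are positive for either incident HIV or incident HBV will be allocated as cases". Neither rule mentions HCV or syphilis, and none of the exclusions in section 4.1.2 names them.

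Under section 4.2.2 (Control Recruitment and Enrollment), potential controls complete the ACASI after donating and become controls only once every test is negative. Sections 4.2.1 and 4.4.1 show that every donation is tested for HCV and, by TPHA, for syphilis.

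**The concern.** Controls should represent the donors from whom the cases arose. Here a syphilis-reactive donor who acquires HIV is a case, while the same donor without HIV or HBV is removed from the controls. Syphilis reactivity is plausibly associated with sexual exposure and HCV reactivity with injecting, and both kinds of exposure are being studied. If those associations are positive, the remaining controls are less exposed than the donors they stand for and the odds ratios rise. Extra controls would not help, because this is bias and not imprecision.

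The rule also closes off one question. Section 3 names the behaviours that donor selection targets: "multiple sexual partners, sexually transmitted diseases, injection drug use, sexual assault". Appendix 7 asks about partners' HIV and hepatitis and about contacts with infected people, but not about the donor's own sexually transmitted infections. TPHA could have supplied some of that information, but every control is TPHA-negative by design.

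**Working it through.** **1. Is the asymmetry real?** Of the section 4.1.2 exclusions, only the deferred-donor criterion and the investigator-discretion criterion could restore symmetry. Section 4.4.1 says that concordant confirmed positive donors are themselves deferred after testing, so the deferred-donor criterion cannot mean deferral on the index test results, or it would remove cases too. The discretion criterion names no marker. The condition therefore applies to controls only.

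**2. The plan's own figures.** Table 8 (300 cases, 900 controls) pairs control and case exposures of 0.15/0.25, 0.20/0.30 and 0.25/0.35. With OR = [p1/(1−p1)]/[p0/(1−p0)], the crude values are 1.889, 1.714 and 1.615, against 1.94, 1.74 and 1.65 stated. The gap of 1.5% to 2.7% cannot be resolved, because the cluster correlation is not given. It has no bearing on this point.

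**3. Common exposure.** Let p be the true exposure in eligible donors, s the share reactive for an excluded marker and e the exposure among reactive donors. The protocol gives neither s nor e, so both are assumed. Exposure among retained controls is (p − s·e)/(1 − s). For 30% of cases against p = 0.20 (true OR 1.714):
- s = 0.002, e = 0.4: 0.1992/0.998 = 0.1996, OR 1.72.
- s = 0.02, e = 0.6: 0.188/0.98 = 0.1918, OR 1.81.

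As a cross-check, let M be the odds ratio between exposure and marker. Solve s·q + (1−s)·r = p0 with odds(q) = M·odds(r); the design then observes odds(p1)/odds(r). For the 0.15/0.25 row (true OR 1.889) and M from 2 to 10:

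| s | OR observed | Inflation |
|---|---|---|
| 0.1% | 1.891–1.896 | 0.1–0.4% |
| 1% | 1.905–1.963 | 0.9–3.9% |
| 2% | 1.922–2.041 | 1.7–8.0% |
| 5% | 1.972–2.297 | 4.4–21.6% |

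If exposure is only 5%, s = 1% with M = 10 gives 6.3%. If every excluded donor were exposed, the 0.15/0.25 row would be inflated by 7.1% at s = 1% and 15.4% at s = 2%.

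**4. Rarer exposure.** For p = 0.03 and a true OR of 1:
- s = 0.005, e = 0.15: 0.02925/0.995 = 0.0294, OR 1.02.
- s = 0.02, e = 0.3: 0.024/0.98 = 0.0245, OR 1.23. This corner needs 0.02 × 0.3/0.03 = 20% of all exposed donors to be reactive.

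For a very rare exposure such as injecting, if a share f of exposed donors is HCV-positive, the OR is multiplied by about 1/(1 − f): 1.05 at f = 5%, 1.11 at 10% and 1.43 at 30%.

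**5. Against sampling error, treating donors as independent.** At 30% versus 20%, the SE of log OR is √(1/90 + 1/210 + 1/180 + 1/720) = 0.151. The largest shift in step 3 for that pair, ln(1.806/1.714) = 0.052, is about one third of an SE. For the 3% exposure, with 9 exposed cases and 27 exposed controls, the SE is √(1/9 + 1/291 + 1/27 + 1/873) = 0.39, and ln 1.23 = 0.21 is about half an SE. At an assumed 0.2% to 1% injecting, only about 2 to 9 of 900 controls would be exposed.

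**6. Syphilis as an exposure.** Reactive controls number 0 by design, so the odds ratio is not estimable.

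**7. Interviews lost.** 900 × s is about 2 to 18 at s = 0.2% to 2%.

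**The case against.** Marker-negative controls are an openly declared comparator, and contrasting infected donors with donors clear on every screening test has some appeal in a study meant to sharpen the donor questionnaire. Neither syphilis, STI history nor injecting is a named hypothesis in section 4 or a named predictor in section 4.9. For the exposure on which the HIV sample size rests, the shift is a fraction of a standard error even at the extreme assumed corner. All of this stands and limits the weight of the point. It does not remove the asymmetry: the protocol gives no reason for adding HCV and syphilis to the control condition and describes no analysis that deals with it. Section 4.8.1 also says the study wants to report on less common exposures, where the bias is proportionally larger.

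Three stronger readings are tempting but not supported:
- A reader might infer that the rule strips out the highest-risk donors. It removes donors reactive for syphilis or HCV, and the protocol gives no risk profile for them. Deferred donors are excluded from both groups.
- A reader might infer that TPHA is the study's only STI measure and is now unusable. Section 4.10.1 links routine health and risk screening data to the study database, and section 3 says donor selection covers sexually transmitted diseases, so some STI answers may exist. TPHA also remains usable for comparisons among cases.
- Section 3 reports that "approximately 2.4 % of those SANBS blood donors with confirmed HIV or HBV infection have been co-infected". A reader might take this as evidence about cases carrying other markers, but it concerns HIV with HBV and says nothing about syphilis or HCV.

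**Conclusion.** The point holds as a control-only eligibility restriction whose bias is upward if syphilis or HCV reactivity is positively associated with the exposure. Its size cannot be determined from the protocol. With 1% or less of donors excluded and marker-exposure odds ratios up to 10, inflation is under about 4% for exposures near 15% or above. It becomes material only if several percent of donors are reactive or the exposure is rare, and estimates for rare exposures will be imprecise in any case. No planned primary contrast is lost, but a case-control odds ratio for syphilis serology is. The weight is minor to moderate; the reason to act is that the correction is nearly free.

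**What to change.** For the main analysis, define controls as donors negative for HIV and HBV on the index donation, and retain potential controls who have completed the ACASI and are reactive only for syphilis or HCV. Make the wording agree in sections 1, 4.1, 4.1.1, both sections numbered 4.2.2, and 4.3. Report the all-marker-negative control set as a sensitivity analysis, so that the planned comparison is still available.

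Record the routine TPHA and HCV results for cases and controls as variables that can be examined as exposures. Do not adjust the behavioural odds ratios for them by default: if reactivity is a consequence of the behaviour, adjustment can itself introduce bias.

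Do not make exclusion of marker-positive cases the main remedy. It makes the criteria symmetric, but it can bias downward when the marker is commoner in cases: with M = 5 and 1% of controls and 5% of cases reactive (assumed), the true 1.889 reads 1.75.

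No new sampling, testing or interviewing is needed. The cost is the text edits and any matching change to participant materials.
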